### **10.2 Secondary Objectives**

For the secondary objectives, engraftment, development of any auto immune side effects, and infections will be treated as binary variables. Chi-square tests will be used to compare each of these 3 outcome variables between the two groups, respectively. A Wilcoxon signed-ranks test will be employed to test the change in absolute lymphocyte (ALC), absolute monocyte counts (AMC), immune cells (T cells CD8, CD4), natural killer cells,  $\gamma\delta$  T-cells, T-reg and MDSCs) at days 15 and 30 post AHSCT from the baseline among each group, respectively. Wilcoxon signed-ranks test will be further used to compare the change of change in ALC, AMC and immune cells between the two groups at days 15 and 30 post- AHSCT, respectively.

Generalized linear mixed models will be employed to compare the change pattern of ALC, AMC and immune cells between the two groups over the entire follow up periods. Time to relapse and overall survival will plotted using the methods of Kaplan and Meier and the log rank test will be used to compare the time to event curves between the two treatment groups.

Lastly, as an explorative objective will also be depth of anti-myeloma response as evaluated by the standard IMWG criteria, including the rate of sCR, and subsequent MRD status for the subjects in sCR.

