**Schema:**

As shown in the schema above:

- 1- Subjects in all groups will receive tetanus vaccine 7-10 days prior to mobilization.
- 2- Subjects in group 1 will have mononuclear cells collected and frozen 7-10 days after tetanus vaccination pre-transplant. These subjects will then receive a CD34+ selected graft on day 0 and autologous donor lymphocyte infusion (DLI) on day +7.
- 3- Subjects in group 2 will receive a standard G-CSF mobilized graft on day 0 without any DLI post-transplant.
- 4- Subjects in all groups will receive G-CSF as subcutaneous injections daily (10 µg/kg) x 5 days starting on day -11 (following the DLI pheresis in the experimental group). Subjects will receive one dose of plerixafor, a stem cell mobilizer, followed by pheresis on the next day to collect G-PBSC graft, with the goal of  $> 6.0 \times 10^6$  CD34+ cells/kg.
- 5- On day of G-PBSC pheresis, the graft in group 2 will be analyzed for CD34, lymphocyte content, and T-reg and MDSCs (cell differential and flow cytometry). Then it will be processed and frozen as per local institutional standards.
- 6- The stem cell product will start to be washed while waiting for the CD34+ content to be known. CD34+ stem cells will then be selected out of the G-PBSC mobilized graft the same day using clinical grade CD34+ magnetic beads and Clinimacs device from Miltenyi as per manufacturer's instructions and as described below. The CD34 content will be analyzed before freezing in liquid nitrogen.
- 7- The subjects in all groups will receive high dose chemotherapy Melphalan at 200 mg/m^2 on day -1.

8- On day 0, subjects in group 1 will receive the thawed CD34+ stem cell graft, while subjects in the group 2 will receive the standard thawed G-PBSC graft. Transplanted CD34+ stem cell dose both groups will be in the range of 2-10 X 10^6/Kg body weight.

9- On day +7 post-transplant, the stored autologous donor lymphocyte product in group 1 will be thawed and infused back to the subjects.

10- **No planned G-CSF post-transplant** (unless medically deemed necessary due to slow engraftment by day 15)

11- Subjects will be followed closely in the hospital until engraftment and resolution of all transplant related toxicities.

12- Subjects will be closely evaluated for any trial related adverse events, specifically: delayed engraftment, auto-immune side effects (autologous graft versus host disease), and infections.

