### **2.3 Immune reconstitution after AHSCT.**

Today's AHSCTs are almost all done with G-CSF mobilized PBSC (G-PBSC), rather than bone marrow grafts based on faster engraftment, decreased risk of infections and days of hospitalization. Early hematopoietic reconstitution of white blood cells, hemoglobin and platelets occur within the first two weeks post AHSCT. However, there is a substantial delay in reconstitution of the non-granulocytic immune components. B-lymphocytes (B-cell) recover to normal numbers within 2-4 months. Natural killer cells (CD56+3- or CD16+3- NK) reached normal values within one month post-transplant. Total T-lymphocyte (T-cell) CD3+ reconstitution occurs within 2-4 months post AHSCT. All patients showed a low CD4/CD8 ratio during the first year post transplant, due both to low numbers of CD4+ cells and elevated numbers of CD8+ cells. The low number of CD4+ cells was due to a persistently low level of naive CD4+CD45RA+ cells. While a high proportion of the CD8+ cells displayed a phenotype compatible with activated T-cells (CD8+DR+) up to 10 months after AHSCT. This seems to be secondary to the intrinsic difference between CD4 versus CD8 regeneration pathways post intensive chemotherapy. CD4 regeneration post intensive chemotherapy is more dependent on thymic function, which starts to regress even in young adults. Therefore CD4 reconstitution post AHSCT is mainly dependent on expansion of mature T-cells in the graft. A clear global

suppression of T-cell proliferative, and cytokine release in response to mitogenic agents *in vitro* has been observed in the first 6-12 months post AHSCT.

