### 2.9 *In-vivo* depletion/modulation of immune suppressive cells improves anti-tumor immune response:

Kline et al. demonstrated that depletion of T-regs enhanced *in vivo* expansion of adoptively transferred tumor specific T-cells, increased their cytokine secretion and their ability to eradicate pre-injected subcutaneous tumors in RAG2-/ (lymphocytes deficient) B16 melanoma animal model. To simulate a transplant model, similar results were observed when C57BL/6 (immune intact) mice irradiated and received adoptive transfer of total or T-reg depleted splenocytes. Collectively the above data showed that T-reg depletion not only enhanced T-cell homeostatic expansion, but also improved their ability to eradicate tumors. Jennifer Ko et al. demonstrated that sunitinib dropped the proportion of MDSC and T reg in the peripheral blood of renal cancer patients, as well as improved T-cell immune function. The use of monoclonal antibodies (CD33 or CD15) for *in vitro* purging of myeloid leukemic cells from PBSC grafts have been attempted before in clinical trials. However, significant delays in neutrophil and platelet engraftment post-transplant have prevented further development of this approach.

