#### **G-CSF post AHSCT will not be given.**

Subjects who show no rise in WBC as a sign of engraftment by day +15 post-transplant are allowed to receive G-CSF at 5 µg/kg daily until absolute neutrophil count is equal or > 500/µL.

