#### *1- Engraftment failure:*

Although quite unlikely based on previous studies with CD34+ selected grafts in AHSCT, in the event of slow engraftment or failure, the subject can receive part or all of his back up CD34+ grafts. No engraftment failure was observed in the two subjects treated on the experimental arm at Emory University.

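### Engraftment is compared as an undated yes/no outcome although the named risk is delay, which gives up much of the power to detect a delay at 10 per arm

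*Combined protocol and SAP*

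**What the plan says.** Section 10.2 of the combined protocol and SAP states that "engraftment, development of any auto immune side effects, and infections will be treated as binary variables", and that "Chi-square tests will be used to compare each of these 3 outcome variables between the two groups, respectively". No day, neutrophil or platelet threshold, or definition of engraftment is attached. The same section plans Kaplan-Meier curves and a log-rank test, but only for relapse and overall survival.

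Elsewhere the risk is described in terms of time:

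- Schema item 12 lists the events to evaluate closely, "specifically: delayed engraftment, auto-immune side effects (autologous graft versus host disease), and infections".
- Section 5.3 is headed engraftment failure but covers both slowness and failure: "in the event of slow engraftment or failure, the subject can receive part or all of his back up CD34+ grafts". It introduces failure with the words "Although quite unlikely based on previous studies with CD34+ selected grafts in AHSCT".
- Section 5.1.10 allows rescue at a fixed day: "Subjects who show no rise in WBC as a sign of engraftment by day +15 post-transplant are allowed to receive G-CSF". That G-CSF continues until the absolute neutrophil count reaches 500/µL.

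Day +15 and the count of 500/µL therefore appear as the trigger and end point for G-CSF, not as the definition of the outcome in section 10.2.

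**The concern.** If the risk is that recovery comes late, an outcome that records only whether it came discards the relevant information. Section 2.3 gives the usual course: "Early hematopoietic reconstitution of white blood cells, hemoglobin and platelets occur within the first two weeks post AHSCT". A shift of a few days against that background may leave nearly every subject classed as engrafted.

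Rescue makes this worse. A subject with no white-cell rise by day +15 may receive G-CSF, and a slow subject may receive back-up cells. Either can end as a yes, and section 10.2 does not say how such subjects count. The back-up reserve is described only for the experimental arm (section 5.1.6), so any masking need not be equal between arms.

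Safety is a primary objective (section 1.1), but section 10.1 gives no safety analysis. The three binary tests in section 10.2 are the only prespecified between-arm safety comparisons. The stopping rule in section 10.4 counts only irreversible toxicity, so a delay that resolves would not trigger it. A real delay could be reported as no difference in engraftment.

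**Working it through.** **The plan's own figure.** The only power statement is in section 10.5: at least 80% for d = 1.36, 10 per arm, two-sided 5%, Mann-Whitney. A noncentral t calculation with n multiplied by the asymptotic relative efficiency 3/π (10 × 0.955 = 9.55 per arm) gives 79.997%. It reproduces, but it concerns the vaccine endpoint. The documents give no power, rate or timing for engraftment.

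**Inputs.** From the documents: 10 per arm, 1:1, α = 0.05, chi-square. Assumed: every subject engrafts; days to engraftment are normal with control mean 12 and SD 2; the experimental arm is later by 2 or 3 days.

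**Step 1: ever engrafted, or a late cut.** With a 3-day delay the experimental mean is day 15, and P(by day 28) = Φ((28 − 15)/2) = Φ(6.5) ≈ 1. Both arms are 10/10 and the power is 0%. The same holds for a 2-day delay.

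**Step 2: engrafted by day 15.** The result depends on whether days are whole numbers (cut at 15.5) or continuous (cut at 15.0). Power is the exact sum over all 10 v 10 tables with uncorrected chi-square p < 0.05.

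| Delay | Cut | Control | Experimental | Chi-square power |
|---|---|---|---|---|
| 3 days | 15.5 | Φ(1.75) = 0.960 | Φ(0.25) = 0.599 | 46% |
| 3 days | 15.0 | Φ(1.50) = 0.933 | Φ(0) = 0.500 | 57% |
| 2 days | 15.5 | Φ(1.75) = 0.960 | Φ(0.75) = 0.773 | 12% |
| 2 days | 15.0 | Φ(1.50) = 0.933 | Φ(0.50) = 0.691 | 21% |

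Simulation with whole days (2,000 trials per scenario) gave 47% and 10%, in line with the first and third rows.

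**Step 3: days to engraftment.** The standardised shift is 3/2 = 1.5 or 2/2 = 1.0. Simulated Mann-Whitney power is 85% and 51%. Log-rank gives 87% and 54%, with a null rejection rate of 6.4% in this setting, so it is slightly liberal.

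**Step 4: sensitivity to the assumptions.** Simulated power with whole days, shown as day-15 chi-square / Mann-Whitney on days:

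| Delay | SD 1.5 | SD 2 | SD 3 |
|---|---|---|---|
| 2 days | 6% / 76% | 10% / 51% | 14% / 28% |
| 3 days | 48% / 98% | 47% / 85% | 30% / 52% |
| 4 days | 93% / 99.8% | 83% / 98.5% | 55% / 76% |

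A day-28 cut gave 0% in every cell.

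**Step 5: the binary as a test of failure.** This is a separate question. With 10/10 in control, 7/10 gives χ² = 20 × (10×3 − 0×7)² / (10×10×17×3) = 3.53, p = 0.060. For 6/10, χ² = 20 × (10×4)² / (10×10×16×4) = 5.0, p = 0.025. Rejection needs 6/10 or fewer, so power is P(X ≤ 6) with X ~ Bin(10, p): 0.1% at p = 0.95, 1.3% at 0.90, 12% at 0.80. Fisher's exact test needs 5/10 or fewer (p = 0.033; 6/10 gives 0.087).

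**The case against.** The strongest reply is that section 10.2 never says ever engrafted. Its three binary outcomes match, in order, the three events in Schema item 12, the first of which is delayed engraftment. Schema item 10 and section 5.1.10 tie slow engraftment to day 15. Read that way, the test does respond to delay, and step 4 shows 55 to 93% power for a 4-day delay. This stands. A reader might infer that the planned test cannot detect the harm at all; the documents do not support that, because they leave the definition open.

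A reader might also set the 0.1 to 1.3% of step 5 against the 85% of step 3. Those describe different harms, rare failure and a shift in timing, and the gap does not measure what dichotomising costs.

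A third tempting inference comes from section 2.9, where "significant delays in neutrophil and platelet engraftment post-transplant have prevented further development of this approach". That approach was CD33 or CD15 antibody purging of leukemic cells. For CD34 selection, section 2.10 reports a randomized myeloma trial that found it safe, and section 5.3 reports no engraftment failure in two treated subjects. Section 2.9 shows that delay matters; it does not predict delay here.

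Failure is also a named risk, for which a yes/no outcome is legitimate, and low power is expected in an exploratory trial of 20. Both are true. Neither is a reason to choose the less sensitive analysis of timing.

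**Conclusion.** The point holds as one of an undefined, dichotomised outcome. The documents name delay as a risk, record engraftment as an undated yes or no, allow rescue that can convert a delay into a yes, and plan no analysis of time to engraftment.

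On the central assumptions, even the favourable day-15 reading loses roughly 30 to 40 percentage points of power against Mann-Whitney (3-day delay: 46 to 57% against 85%; 2-day delay: 12 to 21% against 51%). Under an ever-engrafted or late-cut reading all power to detect delay is lost. The loss is smallest for a large delay with little spread. The mean, SD and delay are assumptions, as is engraftment in every subject, and rescue is not modelled. The ordering of the methods holds across the range tried; the exact percentages do not carry over.

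**What to change.** In section 10.2, replace the chi-square comparison of engraftment with:

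- **Outcomes.** Days from transplant to neutrophil recovery, defined as an absolute neutrophil count at or above 500/µL (the count already used in section 5.1.10), and days to platelet recovery under a prespecified definition. The platelet definition should say how transfusions are handled, since section 5.1.12 provides for platelet transfusion around the day +15 vaccination.
- **Analysis.** Mann-Whitney with non-engrafters ranked last, or log-rank with non-engrafters censored at the end of the observation window. Report the between-arm difference in days with a 95% confidence interval.
- **Rescue.** State how subjects given rescue G-CSF or back-up cells are counted, and tabulate both by arm. Censoring at the moment of rescue should be avoided, because rescue is given for slow recovery.
- **Yes/no rate.** Keep it as descriptive, with a stated day. If it is tested, use Fisher's exact test, since expected counts are small.

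The cost is low but not wording alone. Section 7.0 already schedules blood counts with differential and platelets during hospitalization and at days +7, +15 and +30. However, it shows a single mark for the whole inpatient stay and no count frequency. Dated inpatient counts, or an engraftment date for each lineage, must be added to the case report form. No extra subjects or visits are needed.

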### **1.2 Secondary:**

- 1- To compare post-transplant recovery of innate and adaptive immune cells (CD8, CD4, CD19, NK,  $\gamma\delta$  T-cells), in addition to T-cell phenotype markers between the two arms.
- 2- To compare post-transplant recovery of T-reg and MDSCs between the two arms.
- 3- To compare progression free survival (PFS) at 2 years post-transplant

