#### **4.3 Randomization**

The protocol will randomize subjects to two subsequent arms (10 subjects per arm): group 1 will get a CD34+ selected graft + autologous DLI on day+7, while group 2 will get standard G-CSF mobilized graft only.

The process of a 1:1 randomization between the experimental and control arms. During the registration procedures, study personnel are provided the randomization assignment from the the

IIT Office project coordinator. The 1:1 randomization will be conducted using blocked randomization with blocks of size 2 or 4.

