## **Section 10.0 Statistical Considerations:**

### **10.1 Primary Objectives**

Given the known lack of vaccine response in the first few months post autologous stem cell transplantation, we intend to look for evidence of vaccine response in the experimental arm via increase in tetanus specific T-cell Elispots and anti-tetanus antibody (Elisa) on days 30, 70, 100 and 180 post-transplant. Given the pilot/explorative nature of this trial and the lack of good pre trial assumptions about vaccine response, we will evaluate the vaccine response by Elisa and Elispot on days 30, 70, 100 and 180 will be compared between groups using a Mann-Whitney test.

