### **10.3 Study Design:**

This is a pilot phase II trial with 1:1 randomization between the experimental and control arms.

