### **10.5 Sample Size and Power Consideration**

This is exploratory trial with a total sample size of 20 subjects total (10 subjects in each phase II arm). There is no preliminary data on the primary endpoint of the study (baseline tetanus vaccine response early after transplant). However, it is known that vaccine response in general is muted in the first three months post-transplant. We hypothesize to see a wide difference in Elispot values between the two arms. Two-sided two sample t-test is used to for power calculation. The sample size of 20 will achieve a power of at least 80% to detect an effect size of  $d=1.36$  for a Mann-Whitney test comparing two independent groups at the significance level of 5% assuming that the actual distribution is Normal. Because of the exploratory nature of the study, corrections for multiple comparisons will not be performed. Significance for each test will be set at  $P<.05$ .

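### Section 10.2 assigns a paired test, the Wilcoxon signed-rank, to compare change in cell counts between two independent arms

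*Combined protocol and SAP*

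**What the plan says.** Section 10.2 uses the signed-rank test twice. The first use is for change from baseline within each arm: "A Wilcoxon signed-ranks test will be employed to test the change in absolute lymphocyte (ALC), absolute monocyte counts (AMC), immune cells" and the other listed subsets, at days 15 and 30. The second use compares those changes across arms: "Wilcoxon signed-ranks test will be further used to compare the change of change in ALC, AMC and immune cells between the two groups", on the same two days.

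The design is parallel. Section 10.3 reads "This is a pilot phase II trial with 1:1 randomization between the experimental and control arms", and Section 4.3 adds "The 1:1 randomization will be conducted using blocked randomization with blocks of size 2 or 4". No matching of subjects is defined anywhere.

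Elsewhere the plan treats the arms as unpaired. In Section 10.1 the primary vaccine responses "will be compared between groups using a Mann-Whitney test", and the power statement in Section 10.5 is "for a Mann-Whitney test comparing two independent groups at the significance level of 5"%.

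Section 10.2 also plans generalized linear mixed models for the pattern of change between the arms over the whole of follow-up.

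**The concern.** The first use is sound, because each subject supplies both a baseline and a later value. The second is not, because a subject in one arm has no partner in the other. The sentence can be carried out in only two ways. One is to pair subjects arbitrarily, so that the p-value depends on row order. The other is to pool all 20 changes and test them against zero, which tests change over time and not treatment.

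The sentence serves the first two secondary objectives in Section 1.2, on immune-cell recovery and on suppressor cells; the second of these is "To compare post-transplant recovery of T-reg and MDSCs between the two arms". They test the trial's mechanism: Sections 5.7.1 and 5.7.2 predict higher day-15 ALC, a higher ALC/AMC ratio, and lower T-reg and MDSC levels in the experimental arm. If immune cells means the subsets listed in the preceding sentence (CD8, CD4, NK, γδ T-cells, T-reg, MDSC), there are 8 variables on 2 days, or 8 × 2 = 16 between-arm p-values. Section 10.5 applies no multiplicity correction and judges each at P<.05.

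**Working it through.** **Inputs.** 10 subjects per arm, two-sided 5% level and d = 1.36 for the primary endpoint (Section 10.5). The plan gives no effect size or power for the day-15 and day-30 comparisons. The simulations below therefore assume normal change scores with SD 1 and arm differences of 0.8, 1.0 and 1.36 SD, for illustration only.

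**1. The plan's own figure.** Section 10.5 claims at least 80% power for Mann-Whitney at d = 1.36. Scaling the sample by the test's efficiency under normality:

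- effective n per arm = 10 × 3/π = 9.549
- degrees of freedom = 2 × 9.549 − 2 = 17.10
- noncentrality = 1.36 × √(9.549/2) = 2.97
- power from the noncentral t = 0.79997, or 80.0%

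The figure reproduces; simulating the exact test gives 77.6%. It concerns the primary endpoint and does not depend on the disputed sentence.

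**2. Paired reading.** With 10 subjects per arm there are 10! = 3,628,800 ways to pair them, and the plan picks none. Three simulated data sets (d = 1.36) were each re-paired 5,000 times:

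| Data set | Mann-Whitney p | Signed-rank p, lowest to highest | Pairings with p<.05 |
|---|---|---|---|
| 1 | 0.0039 | 0.002 to 0.084 | 99.5% |
| 2 | 0.0021 | 0.002 to 0.049 | 100% |
| 3 | 0.105 | 0.002 to 0.557 | 20.3% |

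Mann-Whitney gives one answer per data set. When the evidence is clear (sets 1 and 2), pairing hardly matters. In set 3 it decides the result. The floor of 0.002 is the smallest attainable two-sided value, 2/2^10 = 2/1024.

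Over 20,000 simulated trials:

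| d | Mann-Whitney power | Signed-rank power, one arbitrary pairing | Two pairings disagree on P<.05 |
|---|---|---|---|
| 0.8 | 34.9% | 34.1% | 15.4% |
| 1.0 | 50.9% | 49.8% | 16.9% |
| 1.36 | 77.7% | 75.1% | 13.6% |

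With no arm difference and pairing blind to outcome, the signed-rank test rejected in 5.0% of trials.

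**3. Pooled reading.** With identical arms and a common fall of 1 SD, a signed-rank test on all 20 changes rejects in 98.7% of trials. It detects the fall and says nothing about treatment.

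**4. Unequal arms.** With 10 against 9, the differences cannot be formed and the paired test cannot be run. Unequal numbers are realistic: under Sections 5.1.6 and 5.6, subjects who miss the day-1 collection minimum leave the experimental arm or move to arm 2.

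**5. Does blocking create pairs?** No. Blocks of 2 or 4 balance numbers over time. A block of 4 holds two subjects per arm with no unique partner, and the plan does not carry block into any analysis.

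**The case against.** The strongest reply is that signed-ranks is a slip for rank-sum. The sentence says the comparison is between groups, and Sections 10.1 and 10.5 name Mann-Whitney for the same two arms, so a competent analyst would probably run the right test. That is plausible, but the document still specifies a paired test. The analyst must follow it or depart from it after the data are in.

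A second reply is that little depends on it. The endpoints are secondary, the trial is an exploratory pilot of 20, and no sample size or stopping rule rests on this test. The mixed models also compare the same variables between arms. This limits the damage. However, those models cover the entire follow-up and no day-15 or day-30 contrast is specified, so the stated test at those days remains the faulty one.

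A third reply is that, with equal arms and a blind pairing, error control holds and power falls by only about 1 to 3 points. This stands. The harm lies in dependence on an unspecified pairing, which could even be chosen after seeing the results.

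The pooled reading is also unlikely, because it ignores the words about comparing groups. The 98.7% should be read as showing that this alternative offers no escape, and not as an expected error rate.

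**Conclusion.** The concern holds. A paired test is assigned to an unpaired comparison, contrary to the plan's own description of the arms. Under the illustrative assumptions, significance would depend on the arbitrary pairing in about 14 to 17% of trials, most visibly when the evidence is borderline. Those percentages would change with other distributions or effect sizes; the mismatch between test and design would not. The primary analysis, the sample size and the within-arm use of the signed-rank test are unaffected. The text should be corrected before any analysis of these endpoints.

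**What to change.** Replace the between-group sentence in Section 10.2 with:

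*Each subject's change from baseline in ALC, AMC and immune cells at days 15 and 30 will be compared between the two groups with the Wilcoxon rank-sum (Mann-Whitney) test.*

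Keep the signed-rank test for change within each arm only. This brings Section 10.2 into line with Sections 10.1 and 10.5, works with unequal arms, and needs no extra subjects, visits or assays. It costs one sentence and changes no stated figure.

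An analysis of covariance of the day-15 or day-30 value on arm and baseline would also be valid in principle. It is optional: it replaces a rank test with a model for cell counts at 10 per arm and targets a different quantity, so it should be chosen deliberately and its scale specified in advance.

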**Abstract:**

Because curative therapy for multiple myeloma is not yet available, the treatment goal is to produce lengthy asymptomatic disease remissions. High dose chemotherapy with autologous hematopoietic stem cell transplant (AHSCT) provides optimal remission outcomes, and is the current standard of care for transplant eligible patients. However, some patients experience early relapse. One possible explanation for early relapse is poor immune recovery after high dose chemotherapy given before AHSCT. Harvesting an autologous transplant graft product from circulating blood is facilitated by administration of granulocyte colony stimulating factor (G-CSF) to mobilize large numbers of hematopoietic stem cells into the circulation. The cells are collected from the blood with apheresis and stored until the transplant. Our preliminary studies show that immune suppressor cells are also mobilized and collected in the graft product. Depletion of these suppressor cells in the graft before transplant provided enhanced T-cell reactivity to allogeneic antigens and lymphocyte homeostatic expansion. The hypothesis is that depleting majority of immune suppressive cells from G-PBSC graft in vitro in the setting of AHSCT will tip the balance towards accelerated lymphocyte expansion in-vivo, which will be reflected in high ALC numbers on day 15 ( $>500/\mu\text{l}$ ). The goal is to achieve this depletion via selection and infusion of CD34+ cells, thereby eliminating MDSC's and T-reg's which have an immunosuppressing effect on immune reconstitution. This pilot randomized Phase II trial (10 subjects per arm) will compare immune reconstitution following transplantation of an autologous mobilized graft product to reconstitution following transplantation of a mobilized graft product followed by an autologous lymphocyte infusion collected prior to G-CSF mobilization. All subjects will receive tetanus vaccines pre and post-transplant. The primary end point will be tetanus vaccine immune responses post-transplant.

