### **5.7 Immuno-Correlative Laboratory Studies**

5.7.1      Laboratory studies to determine the general immunologic benefit of depleting immune suppressive cells from G-PBSC grafts.

The recovery of ALC and AMC will be recorded at days 15(+/-3) and 30 (+14) post-transplant, as surrogates for immune recovery and predictors of relapse and survival. These values will be obtained as part of the standard clinical care of these subjects post AHSCT. ALC/AMC ratio represents a surrogate for the balance between the host adaptive immune response versus tumor microenvironment immune suppression, as has been shown in the background section. The hypothesis is that depleting majority of immune suppressive cells from G-PBSC graft in the setting of AHSCT will tip the balance towards accelerated lymphocyte expansion *in-vivo*, which will be reflected in high ALC numbers on day 15 (>500/ $\mu$ l). The above intervention is hypothesized to lead to minimum AMC expansion by day 15 post AHSCT, leading to a high ALC/AMC ratio (>1). Such effect may jeopardize self-immune tolerance and trigger an auto-immune reaction or auto-GVHD. The development of autoimmune side effects in the context of cancer immunotherapy has been associated with augmented anti-tumor immune response and survival advantage. This was demonstrated in the use of CTLA4 (Cytotoxic T-Lymphocyte Antigen) blockade in renal cell carcinoma.

5.7.2      Laboratory studies to determine phenotypic recovery of immune cells post AHSCT.

The phenotypic recovery can play a role in cancer immune surveillance and tolerance, specifically T-cells (CD8, CD4), B cells, NK cells,  $\gamma\delta$  T-cells, regulatory T-cells (CD4/CD25+/FOXP3+/CD26-) and MDSCs (CD33+/CD11b+/HLADR low/CD14 low/CD15+/-). These recovery patterns of immune phenotype data collected between the experimental group and the control group in the trial will be compared. PBMCs will be collected for these subjects on day of graft pheresis, +15 (+/-3), +30 (+14), +70(+14, 7-10 days post last tetanus vaccine), +100 (+/-10), and day 180(+30/-7) post-transplant. The number/proportion of MDSCs and T-reg are hypothesized to be much lower in the experimental group compared with the control group.

Subject's blood Samples (70 mls) will be collected on days: Pre-G-CSF, PBSC graft day, days +15 (+/- 3), +30 (+14), +70 (7-14 days post last tetanus vaccine), +100 (+/- 10), and day 180(+/-10) post-transplant.

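### The day-15 predictions, ALC above 500/µl and ALC/AMC above 1, have no matching analysis in Section 10.2, and the planned change-from-baseline comparison may be less precise than a comparison of baseline-adjusted values

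*Combined protocol and SAP*

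**What the plan says.** The Abstract and Section 5.7.1 both predict accelerated lymphocyte expansion "which will be reflected in high ALC numbers on day 15", with a threshold of 500/µl. Section 5.7.1 adds that monocyte expansion should be minimal by day 15, "leading to a high ALC/AMC ratio (>1", that is, above 1. Section 2.6 gives the reason for these cut-offs: it cites reports linking a day-15 ALC of 500/µl, and a day-15 ALC/AMC ratio above 1.0, to better survival after transplant.

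The data are planned for: "The recovery of ALC and AMC will be recorded at days 15(+/-3) and 30 (+14) post-transplant".

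Section 10.2 is the only analysis text for these counts. It plans three things:

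- within-arm signed-rank tests of change "at days 15 and 30 post AHSCT from the baseline among each group, respectively";
- a between-arm test, also named as a signed-rank test, to "compare the change of change in ALC, AMC and immune cells between the two groups at days 15 and 30";
- a longitudinal model: "Generalized linear mixed models will be employed to compare the change pattern of ALC, AMC and immune cells between the two groups", over all follow-up.

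The sample size is a "total sample size of 20 subjects total (10 subjects in each phase II arm". Section 10.5 claims a "power of at least 80% to detect an effect size of $d=1.36$ for a Mann-Whitney test". That claim is made for the vaccine-response (Elispot) comparison, not for ALC.

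**The concern.** The hypothesis concerns where the counts stand on day 15, and how ALC stands relative to AMC. The day-specific analyses concern how far each count has moved from baseline, taken separately. Neither a test of change in ALC nor a test of change in AMC yields a result for their ratio, and neither gives the number of subjects above 500/µl. A reader of the final report could not tell whether the day-15 predictions were borne out.

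There is also a question of efficiency. A change score carries the variance of a count taken before mobilisation and melphalan. If that count says little about the day-15 count, subtracting it adds noise, which 10 subjects per arm can ill afford.

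**Working it through.** **1. Hypothesis against analysis.**

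| Quantity predicted | Where stated | Analysis in Section 10 |
|---|---|---|
| Day-15 ALC above 500/µl | Abstract, 5.7.1 | Change in ALC at days 15 and 30; trajectory model. No threshold. |
| Day-15 ALC/AMC above 1 | 5.7.1 | None. AMC change is tested separately from ALC change. |

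This gap needs no assumption about the data.

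**2. The plan's own power figure.** Inputs from Section 10.5: 10 per arm, d = 1.36, two-sided 5%, Normal data. With a noncentral t and n scaled by the Mann-Whitney asymptotic relative efficiency 3/π, power is 79.997%, which reproduces the stated 80%. Simulating the exact Mann-Whitney test gives about 78%. I use the exact test below. The d is a benchmark only, because the documents give no effect size for ALC.

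**3. Change against value.** Let k = SD(baseline)/SD(day 15), and let ρ be the correlation between the two. Randomisation gives both arms the same expected baseline, so the expected between-arm difference is the same for change as for the day-15 value. Simulation agrees: about 1.36 SD in both cases. The variances differ:

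Var(change) = SD(day 15)² × (1 + k² − 2ρk)

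This exceeds the variance of the day-15 value when k² > 2ρk, that is, when ρ < k/2. The standardised effect on change is d_change = 1.36/√(1 + k² − 2ρk). For example, k = 1 and ρ = 0 give 1.36/√2 = 0.962.

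**4. Power, 10 v 10, exact Mann-Whitney.** Both k and ρ are assumptions. The unadjusted day-15 value has about 78% in every row.

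| k | ρ | d_change | Power on change |
|---|---|---|---|
| 0.5 | 0 | 1.216 | 68% |
| 0.5 | 0.3 | 1.395 | 80% |
| 0.5 | 0.5 | 1.570 | 88% |
| 0.5 | 0.7 | 1.834 | 96% |
| 1 | 0 | 0.962 | 48% |
| 1 | 0.3 | 1.149 | 63% |
| 1 | 0.5 | 1.360 | 77% |
| 1 | 0.7 | 1.756 | 94% |
| 2 | 0 | 0.608 | 22% |
| 2 | 0.5 | 0.785 | 34% |
| 2 | 0.7 | 0.917 | 44% |

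**5. Adjusting instead of subtracting.** Rank ANCOVA of the day-15 value on the baseline value has about 78%, 81%, 87% and 95% power at ρ = 0, 0.3, 0.5 and 0.7, with size about 5%. These figures do not depend on k, because ranking the baseline removes its scale. In the table, change is ahead by at most 1 point (k = 0.5, ρ = 0.5 or 0.7). Over all settings tried the deficit was about 2 points at most.

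**6. Testing the threshold.** Suppose the cut-off lies midway between the arms, so that each arm's mean is 1.36/2 = 0.68 SD from it. The proportions above it are then about 25% and 75%, and Fisher's exact test at 10 v 10 has about 43% power. The thresholds therefore belong in description, not in the main test.

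**The case against.** Two stronger readings are tempting. One is that Section 10.2 answers a different question throughout. For the between-arm contrast of means it does not, since change and value share the same expected difference under randomisation. The charge holds only for the ratio, for the two thresholds, and for the within-arm tests, which do not compare the arms at all. The other is that the planned comparison loses power. The documents give no SD for ALC and no correlation, so this holds only if ρ < k/2. Section 2.6 reports that day-15 counts correlated with the cell numbers in the graft, and under Section 5.1.3 group 1's infused lymphocytes come from the subject's own pre-transplant blood. Neither gives ρ, but neither supports assuming it to be near zero.

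The mixed model also deserves credit. It can take the day-15 counts as outcomes, so it would be wrong to say that only change scores are used. It names no day-15 contrast, however, and omits the ratio.

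Importance is limited. Neither ALC nor the ratio is listed among the objectives in Sections 1.1 to 1.3, the trial is exploratory, and no primary conclusion or stopping rule uses this comparison.

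The power figures describe a Mann-Whitney test on change, which is the nearest valid two-sample reading. Section 10.2 names a signed-rank test, which is paired and cannot compare independent arms. That is a separate fault. Correcting the test name alone would leave the ratio and the thresholds unanalysed.

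**Conclusion.** The concern stands in limited form. The ALC/AMC ratio and both day-15 thresholds appear in no analysis, although the protocol states them as its prediction and the counts are recorded. This rests on the text alone.

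The loss of precision is conditional. Change is worse than the unadjusted value when ρ < SD(baseline)/(2 × SD(day 15)), equal at that point, and better above it. At the borrowed benchmark of d = 1.36 with Normal data, the possible cost ranges from severe (22% against 78% at k = 2, ρ = 0) to none (96% against 78% at k = 0.5, ρ = 0.7). The case for changing the method does not depend on which applies, because baseline adjustment is close to the better of the two in every setting tried. The change should be made, but the point bears on secondary analyses and not on the primary vaccine-response comparison.

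**What to change.** In Section 10.2:

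- Compare the day-15 and day-30 values of ALC, AMC, ALC/AMC and each listed immune-cell subset between arms by rank ANCOVA on the pre-transplant value, with an effect estimate and 95% CI. State which pre-transplant measurement serves as baseline. Section 7.1 already lists a CBC with differential and pre-vaccine immunocorrelative blood. State also how a zero monocyte count is handled in the ratio.
- Report the number per arm with ALC above 500/µl and with ALC/AMC above 1 on day 15, with exact CIs, as description.
- Keep change from baseline as description, and keep the mixed model.

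The immune-cell subsets must stay in the day-specific comparisons because they serve secondary objectives 1 and 2 in Section 1.2. Replacing the planned test with one on ALC, AMC and the ratio alone would drop them.

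The cost is a wording change and a little more analysis, with no new data. The statistical price is about 2 points of power at most against change, when the correlation is high and the baseline SD is small.
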